## APPENDIX 6: DERIVATION OF COMPOSITE MRI ENDPOINTS (FOR EACH SUBJECT, AT EACH TIMEPOINT)

### Muscle categorization

Each muscle is categorized into one of three categories:

- A. 'Normal' muscles are normal appearing (low MFI and MFF, muscle likely unaffected by disease)
- B. 'Affected' muscles have a likely disease involvement (intermediate MFI and MFF)
- C. 'End-stage' corresponds to that more than 50% of the muscle tissue has been replaced by fat, and most of the functional capacity is likely lost

Muscle category	MFF criteria	MFI criteria	
A. Normal	MFF < 10%	AND	MFI < 10%
B. Affected	MFF < 50%	AND	MFI ≥ 10%
C. End-stage	MFF ≥ 50%	-	-

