### Statistical inclusion parameters

The muscle categorization and quality control results are summarized in 3 statistical inclusion parameters which will be provided for each muscle:

- Statistical Inclusion Category: Can take the values **A**, **B** or **C**, which correspond to 'Normal', 'Affected' and 'End-stage'. Abbreviated  $SI_{cat}$  in equations.
- Statistical Inclusion Cross-sectional: Can take the values **0** or **1** (0 if there are major signal quality issues indicating unreliable measurement, 1 otherwise). Abbreviated  $SI_{cross}$  in equations.
- Statistical Inclusion Longitudinal: Can take the values **0** or **1** (0 if there are any signal quality issues, including minor, 1 otherwise). Abbreviated  $SI_{long}$  in equations.

Note: In general, if a SI parameter is 'Unable to Assess', 'NA' or '0', that muscle should be excluded from the corresponding data analysis. As for other muscle measurements, the SI parameters will have a corresponding 'Quality Issues' column – these columns may be ignored.

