### Longitudinal analysis

For longitudinal analysis of disease progression, we only want to include muscles that have category 'B' at baseline – the rationale being that inclusion of Normal appearing muscles (likely not affected by disease) or End-stage appearing muscles (likely not much function left) would only add noise and uncertainty to the analysis of longitudinal changes. Hence:

- If the muscle category is A, C or NA at baseline, the muscle should not be included in longitudinal analysis.
- If the muscle category is B at baseline, the muscle should be included in longitudinal analysis.

We include quality control SI parameters from both timepoints to ensure that we remove a muscle from the calculation if it's unanalyzable in any or both timepoints. For cleaner equations, we combine the statistical

inclusion parameters for the two timepoints here:

$$SI_{long}^{comb} = SI_{long, tp1} \cdot SI_{long, tp2}$$

The absolute change in total LMV, MFI and MFF between timepoint 1 (tp1) and timepoint 2 (tp2) becomes:

$$\begin{aligned}\Delta LMV_{tot} &= \sum_{i \in SI_{cat, tp1=B}} SI_{long, i}^{comb} \cdot (LMV_{i, tp2} - LMV_{i, tp1}) \\ \Delta MFI_{tot} &= \frac{\sum_{i \in SI_{cat, tp1=B}} SI_{long, i}^{comb} \cdot MFI_{i, tp2} \cdot LMV_{i, tp2}}{\sum_{i \in SI_{cat, tp1=B}} SI_{long, i}^{comb} \cdot LMV_{i, tp2}} - \frac{\sum_{i \in SI_{cat, tp1=B}} SI_{long, i}^{comb} \cdot MFI_{i, tp1} \cdot LMV_{i, tp1}}{\sum_{i \in SI_{cat, tp1=B}} SI_{long, i}^{comb} \cdot LMV_{i, tp1}} \\ \Delta MFF_{tot} &= \left( 1 - \frac{\sum_{i \in SI_{cat, tp1=B}} SI_{long, i}^{comb} \cdot LMV_{i, tp2}}{\sum_{i \in SI_{cat, tp1=B}} SI_{long, i}^{comb} \cdot TMV_{i, tp2}} \right) - \left( 1 - \frac{\sum_{i \in SI_{cat, tp1=B}} SI_{long, i}^{comb} \cdot LMV_{i, tp1}}{\sum_{i \in SI_{cat, tp1=B}} SI_{long, i}^{comb} \cdot TMV_{i, tp1}} \right)\end{aligned}$$

The reason we only include the muscle category parameter from timepoint 1 is that we want to make sure to follow a muscle that is 'Affected' at baseline/tp1, even if it progressed into 'End-stage' at follow-up/tp2. A subject with no analyzable muscles should not be included in longitudinal analysis (this can be ensured by removing any subjects with total LMV = 0).

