### Exclusion criteria for longitudinal composite scores

The longitudinal composite observations of relative change in LMV are sensitive to low overall LMV. Therefore, criteria are required for exclusion of such observations. To ensure that the relative change in LMV is reliable LMVref needs to fulfill one of the below:

- Be at least 25 cl and consist of measurements from at least 2 muscles.
- Be at least 50 cl with measurements from at least one muscle.

These criteria apply for all longitudinal composite measurements.

- (1) If a subject's individual muscles couldn't fulfil both bullets above, the subject's change from reference time point in longitudinal composite scores for LMV (L), LMV (%), MFF and MFI should be set to missing. Here, LMVref refers to LMV at reference time point, such as reference screening, and cl means 0.01 liter.
- (2) If a subject's individual muscles could fulfil at least one of the two bullets above, the subject's change from reference time point in longitudinal composite scores for LMV (L), LMV (%), MFF and MFI should not be set to missing.
- (3) The first bullet above refers to at least 2 muscles with a combined LMVref (L) of at least 0.25 liter.

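### The MRI muscle categories in SAP Appendix 6 do not cover muscles with MFF from 10% to below 50% and MFI below 10%, and as written these muscles enter no longitudinal MRI composite

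*SAP*

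**What the plan says.** In SAP Appendix 6, under Muscle categorization, the text promises that "Each muscle is categorized into one of three categories". The table gives the criteria: A (Normal) is "MFF < 10% AND MFI < 10" percent; B (Affected) is "MFF < 50% AND MFI ≥ 10" percent; C (End-stage) is MFF of 50% or more, with no MFI condition. In words, A is low on both measures, and B reads "Affected' muscles have a likely disease involvement (intermediate MFI and MFF".

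Under Statistical inclusion parameters, the list of codes is closed: "Statistical Inclusion Category: Can take the values A, B or C". The note there adds that "if a SI parameter is 'Unable to Assess', 'NA' or '0', that muscle should be excluded from the corresponding data analysis".

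Under Longitudinal analysis, only B at baseline counts: "If the muscle category is A, C or NA at baseline, the muscle should not be included in longitudinal analysis". The reason given is that normal-appearing muscles are probably unaffected and end-stage muscles have little function left, so both would add noise. The formulas for absolute change in total LMV, MFI and MFF, and for relative change in LMV, all sum over muscles that are B at timepoint 1.

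Under Exclusion criteria for longitudinal composite scores, a subject's composite changes are kept only if the reference LMV meets one of two conditions. The first is "Be at least 25 cl and consist of measurements from at least 2 muscles"; the second is at least 50 cl from at least one muscle.

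**The concern.** A rule presented as a complete classification has an uncovered region. A muscle there has a fat fraction too high for Normal and too low for End-stage, so neither stated reason for exclusion applies to it. It is still filtered out of all four longitudinal formulas.

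Two things are at stake. First, the composites would omit some muscles that already show fat replacement, although replacement of muscle by fat on MRI is itself a listed exploratory endpoint (SAP section 1.3.3). Second, losing a muscle lowers both the reference LMV and the muscle count. A subject can then fail the minimum-volume rule and have the longitudinal composites set to missing. Only 14 subjects were enrolled (protocol section 4.1).

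**Working it through.** **1. Coverage of the criteria.** The inputs are the three rows of the categorization table. For a muscle with 10% <= MFF < 50% and MFI < 10%:
- A fails, because MFF is not below 10%.
- B fails, because MFI is not at least 10%.
- C fails, because MFF is not at least 50%.

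The rules were applied to every (MFF, MFI) pair from 0 to 99.9% in steps of 0.1 point, 1,000,000 pairs in all: 10,000 meet A only, 450,000 B only, 500,000 C only, 40,000 none, and no pair meets two. The uncovered pairs form exactly the rectangle above. Boundary cases: (9.9, 9.9) is A; (10, 9.9), (30, 8) and (49.9, 9.9) have no category; (49.9, 10) is B; (50, 5) is C. The 4% share of the grid is geometric and does not estimate the share of muscles affected.

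**2. Can a muscle lie there?** The Appendix 6 total formulas take MFF as 1 - LMV/TMV, and weight MFI by lean volume. They are separate quantities, so nothing in the SAP rules the combination out.

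**3. Effect on LMV change (invented values).** Take two B muscles totalling 30 cl, each losing 1%, and one 60 cl gap muscle losing 5%. The two B muscles pass the first volume condition. The printed relative formula is an unweighted sum of each muscle's relative change:
- Without the gap muscle: -1% + -1% = -2%.
- With it: -1% + -1% + -5% = -7%.

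Absolute change:
- Without: 30 x -1% = -0.3 cl.
- With: -0.3 + (60 x -5%) = -0.3 - 3.0 = -3.3 cl.

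Because the relative formula is a sum, adding any muscle that loses volume makes it more negative.

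**4. Effect on all the composites (second invented subject).** MFF per muscle is assumed to be 1 - LMV/TMV. TMV is held constant.

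| Muscle | TMV, cl | LMV, cl | MFI, % | Baseline MFF |
|---|---|---|---|---|
| 1 (B) | 40 | 32 to 31 | 15 to 16 | 20% |
| 2 (B) | 30 | 24 to 23.5 | 14 to 14.5 | 20% |
| 3 (gap) | 60 | 42 to 39 | 8 to 9 | 30% |

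| Composite | As written (1, 2) | With muscle 3 |
|---|---|---|
| Reference LMV | 56 cl | 98 cl |
| Change in LMV | 54.5 - 56 = -1.5 cl | 93.5 - 98 = -4.5 cl |
| Change in MFF | 56/70 - 54.5/70 = +2.1 points | 98/130 - 93.5/130 = +3.5 points |
| Change in MFI | 836.75/54.5 - 816/56 = +0.78 points | 1187.75/93.5 - 1152/98 = +0.95 points |

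**5. Minimum-volume rule.** A subject with one 20 cl B muscle and one 60 cl gap muscle has, as written, 20 cl from one muscle and fails both conditions. Counting the gap muscle gives 20 + 60 = 80 cl from two muscles, which meets both.

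**6. Closing the gap.** Two edits each give all 1,000,000 pairs exactly one category. With B = MFF < 50% AND (MFF >= 10% OR MFI >= 10%), gap muscles enter the longitudinal composites. With A = MFF < 50% AND MFI < 10%, they stay out, by explicit rule.

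**The case against.** The strongest reply is that the SAP does not say where these muscles belong. Its wording for B asks for intermediate values of both measures, and a gap muscle has low MFI. A reader might infer that the SAP's own description makes such a muscle Affected; it does not. The description of A does not fit either, and an edit that places these muscles in A is equally exhaustive. This stands. Placing them in B is a recommendation, resting on the fact that neither stated reason for exclusion fits them.

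The second reply is that the gap may be empty, or handled by an unstated rule. The service provider derives the scores (SAP section 3.4.2), and coding these muscles as B would remove the effect. This also stands, and it limits the claim to what the text prescribes.

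Third, a reader might infer that a subject who fails the volume rule is lost to the study. The rule sets only the changes in the longitudinal composites to missing. Cross-sectional composites include muscles regardless of category, the individual-muscle summaries in SAP section 3.4.2 state no category filter, and all other analyses keep the subject.

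Two further inferences are unsupported. A volume-weighted average would give -3.7% with the gap muscle in step 3, (30 x -1% + 60 x -5%)/90, against -1.0% without it, but the SAP's relative formula is an unweighted sum. Nor do the documents define MFI as a particular pattern of infiltration, so nothing can be concluded about which type of disease is followed.

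**Conclusion.** The criteria contradict the statement that every muscle receives one of three categories, and as written a gap muscle at baseline contributes to none of the longitudinal LMV, MFF and MFI composites. This is an error in a stated rule and is established from the text alone. A muscle that is B at baseline and moves into the region later is unaffected, because only the baseline category is used.

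The size is not established. It is zero if no muscle lies in the gap or if the provider coded such muscles B. Otherwise it depends on their number, volume and change, none of which the documents give. The worked figures are illustrations on invented values.

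The point is worth correcting but limited in reach. The composites are exploratory, the study has no formal testing (protocol section 2.3, SAP section 2.4), and no primary or secondary result changes.

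**What to change.** In Appendix 6, define B as MFF < 50% AND (MFF >= 10% OR MFI >= 10%), leaving A and C as they are. If the sponsor prefers to keep these muscles out, the SAP should say so and give the reason.

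Ask the MRI provider how muscles in this region were coded, and write that rule down. Report how many muscles and subjects change category, and how many subjects change status under the volume rule.

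SAP section 5 already describes how the follow-up MRI results are presented, and the study is open-label, so a change now is post hoc. Present the revised composites as a labelled analysis beside those under the existing rule. Document the change in the SAP and justify it in the CSR, as protocol section 10.1 provides.

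The cost is one line of text, a rerun of the composite calculation on existing measurements, a small amount of extra reporting, and the post hoc label. No new data are needed.

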### Quality control of measurements

Trained anatomical imaging experts evaluate the signal quality in each muscle. If a muscle is not analyzable, that muscle is marked as not analyzable and no measurements will be extracted from it. For cross-sectional analysis minor quality issues are accepted, but not for longitudinal analysis. Hence, as seen below, we'll use different statistical inclusion parameters depending on if we are doing a cross-sectional or longitudinal analysis.

### Statistical inclusion parameters

The muscle categorization and quality control results are summarized in 3 statistical inclusion parameters which will be provided for each muscle:

- Statistical Inclusion Category: Can take the values **A**, **B** or **C**, which correspond to 'Normal', 'Affected' and 'End-stage'. Abbreviated  $SI_{cat}$  in equations.
- Statistical Inclusion Cross-sectional: Can take the values **0** or **1** (0 if there are major signal quality issues indicating unreliable measurement, 1 otherwise). Abbreviated  $SI_{cross}$  in equations.
- Statistical Inclusion Longitudinal: Can take the values **0** or **1** (0 if there are any signal quality issues, including minor, 1 otherwise). Abbreviated  $SI_{long}$  in equations.

Note: In general, if a SI parameter is 'Unable to Assess', 'NA' or '0', that muscle should be excluded from the corresponding data analysis. As for other muscle measurements, the SI parameters will have a corresponding 'Quality Issues' column – these columns may be ignored.

### Whole-body combined measurements

#### Cross-sectional analysis

MRI-based measurements from multiple muscles is combined to obtain global measurements of disease affection for correlation to disease severity or functional test scores in cross-sectional data:

$$LMV_{tot} = \sum_{i \in muscles} SI_{cross,i} \cdot LMV_i$$

 Note that AMRA® Researcher is for research purposes only, and the names of these categories do not correspond to any form of diagnosis.

$$MFI_{tot} = \frac{\sum_{i \in muscles} SI_{cross,i} \cdot MFI_i \cdot LMV_i}{\sum_{i \in muscles} SI_{cross,i} \cdot LMV_i}$$

$$MFF_{tot} = 1 - \frac{\sum_{i \in muscles} SI_{cross,i} \cdot LMV_i}{\sum_{i \in muscles} SI_{cross,i} \cdot TMV_i}$$

MFFtot is likely to correlate best with functional tests as it reflects global muscle-to-fat replacement, while interpretation of total LMV at only one timepoint requires reference data for normal total LMV that is not available at the moment. Note that muscles are included regardless of category (A, B and C). A subject with no analyzable muscles should not be included in the cross-sectional analysis. The included muscles depend on the function of interest. Some examples are given below.

Functional test	Included muscles
Global tests: 
 
Disease severity / Whole-body function
 
FSHD TUG
 
	All muscles
Focused walk tests: 
 
Timed Up and Go (TUG) test
 
	Leg muscles: 
 
Quadriceps
 
Hamstrings
 
Adductors
 
Tibialis Anterior
 
Gastrocnemius Medialis
 

Reach tests: 
 
Reachable workspace (RWS) test
 
	Arm, rotator cuff, and torso muscles: 
 
Biceps Brachii
 
Triceps Brachii
 
Deltoides
 
Pectoral Muscles
 
Rhomboideus Major
 
Latissimus Dorsi/Teres Major
 
Supraspinatus
 
Infraspinatus
 
Teres Minor
 
Subscapularis
 
Serratus Anterior
 

### Longitudinal analysis

For longitudinal analysis of disease progression, we only want to include muscles that have category 'B' at baseline – the rationale being that inclusion of Normal appearing muscles (likely not affected by disease) or End-stage appearing muscles (likely not much function left) would only add noise and uncertainty to the analysis of longitudinal changes. Hence:

- If the muscle category is A, C or NA at baseline, the muscle should not be included in longitudinal analysis.
- If the muscle category is B at baseline, the muscle should be included in longitudinal analysis.

We include quality control SI parameters from both timepoints to ensure that we remove a muscle from the calculation if it's unanalyzable in any or both timepoints. For cleaner equations, we combine the statistical

inclusion parameters for the two timepoints here:

$$SI_{long}^{comb} = SI_{long, tp1} \cdot SI_{long, tp2}$$

The absolute change in total LMV, MFI and MFF between timepoint 1 (tp1) and timepoint 2 (tp2) becomes:

$$\begin{aligned}\Delta LMV_{tot} &= \sum_{i \in SI_{cat, tp1=B}} SI_{long, i}^{comb} \cdot (LMV_{i, tp2} - LMV_{i, tp1}) \\ \Delta MFI_{tot} &= \frac{\sum_{i \in SI_{cat, tp1=B}} SI_{long, i}^{comb} \cdot MFI_{i, tp2} \cdot LMV_{i, tp2}}{\sum_{i \in SI_{cat, tp1=B}} SI_{long, i}^{comb} \cdot LMV_{i, tp2}} - \frac{\sum_{i \in SI_{cat, tp1=B}} SI_{long, i}^{comb} \cdot MFI_{i, tp1} \cdot LMV_{i, tp1}}{\sum_{i \in SI_{cat, tp1=B}} SI_{long, i}^{comb} \cdot LMV_{i, tp1}} \\ \Delta MFF_{tot} &= \left( 1 - \frac{\sum_{i \in SI_{cat, tp1=B}} SI_{long, i}^{comb} \cdot LMV_{i, tp2}}{\sum_{i \in SI_{cat, tp1=B}} SI_{long, i}^{comb} \cdot TMV_{i, tp2}} \right) - \left( 1 - \frac{\sum_{i \in SI_{cat, tp1=B}} SI_{long, i}^{comb} \cdot LMV_{i, tp1}}{\sum_{i \in SI_{cat, tp1=B}} SI_{long, i}^{comb} \cdot TMV_{i, tp1}} \right)\end{aligned}$$

The reason we only include the muscle category parameter from timepoint 1 is that we want to make sure to follow a muscle that is 'Affected' at baseline/tp1, even if it progressed into 'End-stage' at follow-up/tp2. A subject with no analyzable muscles should not be included in longitudinal analysis (this can be ensured by removing any subjects with total LMV = 0).

Since different number of muscles may be included in each individual patient, and each patient may have different muscle sizes, a relative change in total LMV may be a better endpoint than absolute change in total LMV (for MFI and MFF, absolute change makes most sense since they are fractions). This corresponds to:

$$\Delta LMV_{tot}^{relative} = \sum_{i \in SI_{cat, tp1=B}} SI_{long, i}^{comb} \cdot \left( \frac{LMV_{i, tp2} - LMV_{i, tp1}}{LMV_{i, tp1}} \right)$$

As a start, it makes sense to include all analyzable muscles in the longitudinal analysis, although muscles can also be grouped similarly to the cross-sectional analysis for assessment of longitudinal change of function.

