#### **Composite measures:**

Composite variables, incorporating pre-selected muscles, will be derived for longitudinal analysis of muscle fat fraction, lean muscle volume and muscle fat infiltration (MFFtot, LMVtot, and MFItot respectively). The longitudinal composite observations of relative change in LMV are sensitive to low overall LMV, therefore an exclusion criterium is applied for such observations. See [Appendix 6](#) for derivations and exclusion criteria. The scores will be derived and exclusions applied by scientists at the MRI Service Provider (AMRA Medical Inc.).

Descriptive statistics of MFFtot, LMVtot, and MFItot per visit as well as changes from baseline will be presented for the whole body, as well as muscle regions as applicable. Missing visit observations will be back calculated from provided screening and change from screening values.

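### The change in MFItot mixes within-muscle change in fat infiltration with a shift in lean-volume weights, so it can misstate progression when muscles lose lean volume unequally

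*SAP*

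**What the plan says.** SAP Section 3.4.2 plans composite variables for fat fraction, lean volume and fat infiltration: "Descriptive statistics of MFFtot, LMVtot, and MFItot per visit as well as changes from baseline will be presented for the whole body", and for muscle regions as applicable. The MRI service provider derives the scores under Appendix 6.

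The Longitudinal analysis part of Appendix 6 fixes the muscle set at baseline: "If the muscle category is B at baseline, the muscle should be included in longitudinal analysis". A muscle must also pass quality control at both timepoints. An affected muscle stays in the score "even if it progressed into 'End-stage' at follow-up/tp2".

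Under the words "The absolute change in total LMV, MFI and MFF between timepoint 1 (tp1) and timepoint 2 (tp2) becomes", the change in MFItot is the LMV-weighted mean MFI at tp2 minus the LMV-weighted mean MFI at tp1. The first mean uses LMV at tp2 as weights and the second uses LMV at tp1.

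The exclusion rule for longitudinal composites looks only at reference lean volume and the number of muscles. One way to qualify is: "Be at least 25 cl and consist of measurements from at least 2 muscles". The other is at least 50 cl from at least one muscle. The appendix gives no fixed-weight version of the MFI change and no caution about moving weights.

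**The concern.** Appendix 6 says the longitudinal composite is meant to follow disease progression in affected muscles, and it deliberately keeps muscles that progress to end-stage. Yet a muscle that loses more lean volume than the others also loses weight in the MFI score. The set of muscles is held constant while their influence is not.

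A reader of the MFItot change would naturally take it as average change within the affected muscles. If weight moves from more to less infiltrated muscles between scans, part of the reported change is only that shift. The trial has no control arm in which the same shift would appear. The MRI composites are reported at the second interim analysis (SAP Section 4.1) as well as in the main MRI summaries, so a stable or falling MFItot could be read as stable or improving muscle when the muscles themselves say otherwise.

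**Working it through.** The plan gives no figure for this point, so there is nothing of its own to reproduce. The check evaluates the Appendix 6 formula and splits it into its parts.

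**Inputs from the SAP.** The formula for the change in MFItot; the category B rule (MFF below 50% and MFI at least 10% at baseline); the exclusion rule on reference LMV.

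**Assumed inputs.** All per-muscle values below, because the documents contain none. Each muscle is taken to be category B (so MFF below 50%) and to pass quality control at both scans.

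**Decomposition.** Let w1 and w2 be a muscle's share of total included LMV at tp1 and tp2. Then

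change in MFItot = Σ w1 × (MFI_tp2 − MFI_tp1) + Σ (w2 − w1) × MFI_tp2.

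The first sum is within-muscle change at baseline weights. The second is re-weighting, and it is zero when every muscle loses the same proportion of lean volume.

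**Case 1 in full.** Muscle 1: MFI 12 to 12.5%, LMV 50 to 50 cl. Muscle 2: MFI 40 to 42%, LMV 20 to 15 cl.

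- Baseline: (12×50 + 40×20)/70 = 1400/70 = 20.00
- Follow-up: (12.5×50 + 42×15)/65 = 1255/65 = 19.31
- SAP change: 19.31 − 20.00 = −0.69
- Baseline weights: (0.5×50 + 2×20)/70 = 65/70 = +0.93
- Re-weighting: −0.69 − 0.93 = −1.62

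Reference LMV is 70 cl from two muscles, so the exclusion rule keeps this subject.

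**Other patterns, same arithmetic (LMV in cl, changes in percentage points).**

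| Case | Muscle 1: MFI; LMV | Muscle 2: MFI; LMV | SAP change | Baseline-weighted | Re-weighting |
|---|---|---|---|---|---|
| 1. More infiltrated muscle loses more | 12→12.5; 50→50 | 40→42; 20→15 | −0.69 | +0.93 | −1.62 |
| 2. Same direction, milder | 12→12.3; 50→49.5 | 35→36; 20→18.5 | +0.18 | +0.50 | −0.32 |
| 3. Same direction, very small changes | 12→12.1; 50→49.5 | 30→30.1; 50→48 | −0.04 | +0.10 | −0.14 |
| 4. Equal 10% loss | 12→12.5; 50→45 | 30→31; 50→45 | +0.75 | +0.75 | 0 |
| 5. Less infiltrated muscle loses more | 12→12.5; 50→45 | 40→42; 20→20 | +1.58 | +0.93 | +0.65 |

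MFI rises in both muscles in every row. The SAP change is negative in rows 1 and 3, attenuated in row 2, undistorted in row 4 and inflated in row 5.

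**Break-even.** Take two muscles of equal size, a baseline MFI gap of g points, a uniform MFI rise of d points, and no lean loss in the less infiltrated muscle. The composite change is zero when the other muscle loses the proportion x = 4d/(g + 2d); a larger loss reverses the sign. For g = 18:

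- d = 0.1: 0.4/18.2 = 2.2%
- d = 0.5: 2/19 = 10.5%
- d = 1: 4/20 = 20.0%
- d = 2: 8/22 = 36.4%

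**How often?** Simulation on assumed values used 2 to 20 muscles, baseline MFI 10 to 35% and LMV 0.1 to 1 L, with every MFI rising and no LMV rising. When lean loss was unrelated to MFI, the composite fell in 0 to 9% of subjects. When loss increased with baseline MFI, it fell in 0 to 1% (mean loss 5%, mean rise 1 point), 8 to 15% (15%, 1 point) and 26 to 86% (15%, 0.5 points). The spread shows that the answer depends on the assumptions.

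**The case against.** The strongest defence is that MFItot is a legitimate quantity as written: the average infiltration of the lean tissue present at each scan. Loss of lean tissue belongs to LMVtot and MFFtot, defined beside it, and Appendix 6 singles out MFFtot as the measure of global replacement of muscle by fat. In Case 1 the same output would show LMVtot falling by 5 cl. SAP Section 3.4.2 also requires MFI, LMV and MFF for each muscle location, and the second interim analysis shows all three by location and for the whole body. The endpoints are exploratory, Protocol Section 2.3 and SAP Section 2.4 rule out formal testing, and no decision rule uses MFItot.

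Most of this stands, and it limits the importance of the point. It does not remove it. The companion tables may alert a careful reader to a conflict, but summaries by location across subjects do not allow the composite to be corrected. A difference between two means with different weights is also not what a reader expects from a score meant to follow progression in a fixed set of muscles.

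The objection also stands on realism. Case 1 needs a large loss: with its MFI values the sign reverses once muscle 2 falls below 375/22 = 17.0 cl, a loss of about 15%, and the example uses 25%. The progression rate in Protocol Section 1.1, 1% to 4% per year, is for average strength and not for lean volume. It neither supports nor excludes such a loss in a single muscle.

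**Conclusion.** The point holds in conditional form. The formula lets weights move between scans, so the change in MFItot is not a pure within-muscle change. It understates worsening, and can reverse its sign, when more infiltrated category B muscles lose proportionally more lean volume. It is undistorted under equal proportional loss and overstates worsening under the opposite pattern.

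Three stronger readings are tempting and are not supported:

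- A reader might infer that the composite is biased toward improvement in this trial, and so gives a false favourable signal. Replacement of muscle by fat is the disease course the protocol describes, but neither document says which affected muscles lose lean volume fastest.
- A reader might take a simulated attenuation as the expected size. With 4 to 12 affected muscles and relative lean loss set at 0.1 to 0.3 times MFI, mean changes by the SAP formula against baseline weights ran from 0.308 against 0.450 (1 − 0.308/0.450 = 31.6% lower) to 1.304 against 1.351 (3.5% lower). That setup builds in the adverse pattern, and every mean stayed positive.
- A reader might conclude that the service provider's score is wrong and should be replaced. It answers a different question and can stay.

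All worked values are illustrative; size and frequency in this trial cannot be derived from the documents. Because the endpoint is exploratory and descriptive, this is a cheap improvement of low severity.

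**What to change.** Keep the service provider's MFItot change and add one line to Appendix 6 and to the tables:

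baseline-weighted change in MFI = Σ [SI_long_comb × LMV_tp1 × (MFI_tp2 − MFI_tp1)] / Σ [SI_long_comb × LMV_tp1], summed over muscles in category B at tp1.

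Here SI_long_comb is the existing product of the two longitudinal quality flags. State that any conclusion about progression of fat infiltration within muscles rests on this line. It cannot be negative when every included muscle's MFI rises, and it equals the present formula when proportional lean loss is equal.

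The cost is one formula, one extra table line and a recalculation from per-muscle values already planned for analysis. There are two downsides. The new line may differ from the provider's standard output, which needs a sentence of explanation. It also gives full baseline weight to follow-up MFI in muscles with little lean tissue left, including those that became end-stage. That is a reason to show both lines together.

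### The SAP's relative change in total lean muscle volume adds up per-muscle percentage changes, so it grows with the number of affected muscles and does not measure relative muscle loss

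*SAP*

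**What the plan says.** Appendix 6 of the SAP defines the longitudinal MRI composites. A muscle enters according to its baseline category: "If the muscle category is B at baseline, the muscle should be included in longitudinal analysis". It must also pass quality control at both timepoints, through a flag described as "Statistical Inclusion Longitudinal: Can take the values 0 or 1"; the flags for the two timepoints are multiplied together.

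The absolute change in total LMV is the sum of the differences over these muscles. The appendix then introduces a second version and suggests that "a relative change in total LMV may be a better endpoint than absolute change in total LMV". The reason it gives is that subjects differ in the number and size of the muscles that enter. The expression that follows is the sum, over the same muscles, of the flag times (LMV at timepoint 2 minus LMV at timepoint 1) divided by that same muscle's LMV at timepoint 1.

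The muscle fat infiltration (MFI) and muscle fat fraction (MFF) composites are treated differently. Each is built from ratios of sums, and the appendix remarks that "for MFI and MFF, absolute change makes most sense since they are fractions".

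Under the exclusion criteria for longitudinal composite scores, the SAP adds that "The longitudinal composite observations of relative change in LMV are sensitive to low overall LMV". It requires a reference LMV of at least 25 cl from two or more muscles, or at least 50 cl from one or more. That section lists LMV (%) among the change scores. SAP section 3.4.2 also refers to the relative LMV change as a longitudinal composite, and the second interim analysis (section 4.1) summarises MRI composite scores.

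**The concern.** The relative measure is there so that subjects with different numbers and sizes of muscles can be compared. The printed formula does neither job. It has no normalising denominator, so it rises with the number of category B muscles, and it gives every muscle equal weight whatever its volume.

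As printed, a subject with more affected muscles shows a larger loss for the same rate of disease. The group mean is not a percentage change in muscle volume, and much of the between-subject SD could reflect muscle count alone. The MRI results are descriptive, in a study that enrolled 14 subjects, so that mean and SD are what a reader would take as evidence of muscle loss or preservation.

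**Working it through.** The documents give no worked value for this endpoint, so there is no figure to reproduce. They also give no muscle volumes, loss rates or counts of category B muscles. All such inputs below are illustrative assumptions.

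**Definitions.** For the included muscles i = 1 to k (flag = 1), with baseline volume a_i and follow-up volume b_i:

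- SAP formula: S = sum of (b_i − a_i)/a_i
- Ratio of totals: R = [sum of (b_i − a_i)] / [sum of a_i]
- Mean of per-muscle changes: M = S/k

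The flag is 0 or 1, so it selects muscles and cannot act as a normalising weight.

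**Dependence on muscle count.** If every muscle changes by the same fraction r, then S = k × r, while R = M = r.

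| k | S at r = −2% | S at r = −3% | S at r = −4% |
|---|---|---|---|
| 2 | −4% | −6% | −8% |
| 5 | −10% | −15% | −20% |
| 10 | −20% | −30% | −40% |
| 20 | −40% | −60% | −80% |

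R equals r in every cell. The functional-test table in Appendix 6 names 16 muscles or muscle groups as examples (5 leg; 11 arm, rotator cuff and torso). With those 16, a uniform 3% loss gives 16 × (−3%) = −48%. Any uniform loss above 100/16 = 6.25% gives a value below −100%, which is impossible for a volume.

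**Spread created by count alone.** Let every subject lose exactly 3% in every muscle.

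- k even over 4 to 20 (17 values): mean k = 12, variance (17² − 1)/12 = 24, SD 4.90. S has mean −36% and SD 3 × 4.90 = 14.7 points.
- k even over 4 to 16 (13 values): mean k = 10, variance (13² − 1)/12 = 14, SD 3.74. S has mean −30% and SD 11.2 points.

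R is −3% with SD 0 in both cases.

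**Noise.** Assume no true change and independent error with SD 3% per muscle. The SD of S is 3 × √k: 4.2 points at k = 2 and 13.4 at k = 20. The SD of M is 3/√k: 2.1 and 0.67. Measuring more muscles makes S less precise.

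**Dependence on muscle size (two muscles).**

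| Change | S | R | M |
|---|---|---|---|
| 100 → 100 cl and 5 → 3 cl | 0 − 2/5 = −40% | −2/105 = −1.9% | −20% |
| 100 → 99 cl and 5 → 4.5 cl | −1% − 10% = −11% | −1.5/105 = −1.4% | −5.5% |
| 100 → 102 cl and 5 → 4.5 cl | +2% − 10% = −8% | +1.5/105 = +1.4% | −4% |

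All three cases have 105 cl at baseline from two muscles, so all pass the exclusion rule. In the last, total volume rises and the SAP formula reports a loss.

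**Fit with the rest of the appendix.** A floor on combined baseline LMV stabilises a ratio that has combined LMV as its denominator. It does not stabilise a sum of ratios in which one small muscle can dominate. The MFI and MFF composites are ratios of sums; the relative LMV change alone is not.

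**The case against.** The best reply concedes the algebra and argues that little depends on it.

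- **Status.** The primary endpoint is safety, MRI is exploratory, and the SAP plans no formal tests. Absolute LMV change, MFF, MFI and the individual-muscle results do not use this formula. Section 3.4.2 does not list LMV (%) by name among the tabulated statistics, and the appendix wording about the relative endpoint is permissive. All of this stands and limits the reach. It does not make the formula right: Appendix 6 names LMV (%) as a composite score with its own handling rules.
- **Derivation by the vendor.** The MRI provider derives the scores and may already use a ratio of totals; the exclusion rule would fit that. The documents do not show it. So the error in the printed formula is certain, and an error in the delivered values is not.
- **Exclusion rule.** It applies to all longitudinal composites, so it can be read as a general reliability floor. It is fair to say that the floor does not match the formula, not that the two are logically incompatible.
- **Illustrative inputs.** Exact growth with k needs changes in the same direction; mixed changes partly cancel, though the variance still grows with k. The 5 cl muscle falling by 40% is an extreme case.
- **Choice of remedy.** A mean of per-muscle changes would also remove the dependence on count. It would keep equal weighting of small and large muscles: the sign-reversal example still gives −4% against +1.4%.

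**Conclusion.** The concern holds. As printed, the formula is not a relative change in total LMV, and it brings back the dependence on muscle number that it was introduced to remove. For uniform change, the result is inflated by a factor equal to the number of category B muscles analysable at both timepoints. For unequal muscles, it can differ from the change in the total in size and in sign.

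The algebraic result needs no assumption beyond the formula; the percentages rest on the assumed loss rates, volumes and counts. The error is confined to one exploratory composite, LMV (%). Whether reported values are affected depends on the vendor's derivation, which the documents do not show. In either case the SAP needs correcting: the values are wrong, or the SAP misdescribes how they were obtained.

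**What to change.** In Appendix 6, replace the relative-change expression with

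`100 × sum[SI × (LMV_tp2 − LMV_tp1)] / sum[SI × LMV_tp1]`

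over muscles in category B at baseline, where SI is the combined longitudinal inclusion flag. This is the quantity the SAP names, and it matches the existing floor on combined reference LMV. If a mean of per-muscle changes is preferred, the SAP should name it as such and justify the equal weighting.

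Ask the MRI vendor to state in writing which definition its LMV (%) values use. If it is the printed sum, re-derive the values and any summary already produced from them, including those for the second interim analysis. Reporting the number of included muscles per subject beside the composite would help the reader.

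The cost is one formula in the SAP and a vendor confirmation or a re-derivation from existing per-muscle volumes. No new scans or data collection are needed.
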